## Background and Introduction

---

### Introduction

Residual limb (RLP) and phantom limb pain (PLP) affects most amputees at some point in their life. The incidence of PLP has been estimated to range between 50 – 80%. RLP prevalence has been estimated to be 43%. The peak of onset is bimodal and often appears within the first month and second year after amputation. RLP is more common in the first year after amputation, with PLP becoming the predominate amputee pain complaint after one-year post-amputation.

Both RLP and PLP fall under the umbrella term “post-amputation pain.” While these conditions are frequently found in combination, their clinical features and underlying causes are distinct. PLP is a painful sensation in the distribution of the missing limb. Following amputation, abnormalities at multiple levels of the neural axis have been implicated in the development of PLP; changes include cortical reorganization, reduced inhibitory processes at the spinal cord, synaptic response changes and hyperexcitability at the dorsal root ganglion, and retrograde peripheral nerves shrinkage.

Residual limb pain has been called “neuroma pain” and is mechanistically distinct from PLP. Neuromas may form as early 6-10 weeks after nerve transection, and are thought to produce ectopic neural discharges resulting in severe pain. Evidence suggests RLP and PLP commonly co-occur and patients may struggle to differentiate between these pain types. Risk factors include female sex, upper extremity amputation, pre-amputation pain, residual pain in contralateral limb, and time since amputation.

Depression, anxiety, and stress are known to exacerbate PLP / RLP. Patients experiencing PLP and RLP also experience a higher incidence of indecisiveness, suicidal ideation, and thoughts of self-harm^8. Current guidelines for treatment of PLP and RLP are not standardized. Treatments includes pre-operative analgesia, neuromodulation mirror therapy, imagery, acupuncture, transcranial stimulation, deep brain stimulation, and medications (including, but not limited to: TCAs, SSRIs, gabapentinoids, sodium channel blockers, ketamine, opioids, and NSAIDs). Many agents have been injected in neuromas. These include local anesthetic, phenol, alcohol, and botulinum toxin. These oral, intravenous, and nonpharmacological modalities have demonstrated limited success in the treatment of PLP / RLP. Neuroma cryoablation has been used, but this method of neural destruction poses technical challenges related to cumbersome needle placement and the requirement for time-intensive freeze-thaw cycles.

Conventional RFA has been studied on RLP. Zhang et. al treated 13 patients with painful stump neuromas. The study started with alcohol neurolysis before using ultrasound-guided RFA for refractory cases. The frequency of sharp pain was reduced in all RFA-treated patients.

Kim et. al described a case in which ultrasound-guided RFA was successfully used to treat a sciatic neuroma of an above-knee amputee.

No outcome literature on the effectiveness of C-RFA technology has been published. C-RFA is similar in mechanism to conventional RFA: a thermal lesion is created by applying radiofrequency energy through an electrode placed at a target structure. In C-RFA, a constant flow of ambient water is circulated through the electrode via a peristaltic pump, maintaining a lowered tissue temperature by creating a heat sink. By removing heat from tissues immediately adjacent to the electrode tip, a lower lesioning temperature is maintained, resulting in less tissue charring adjacent to the electrode, less tissue impedance and more efficient heating of target tissue. The volume of tissue heated, and the resultant thermal lesion size is substantially larger with C-RFA, conferring an advantage over conventional RFA. Further, given the spherical geometry and forward projection the C-RFA lesions beyond the distal end of the electrode, the RFA probe can be positioned at a range of possible angles and still capture the target neural structure, whereas more fastidious, parallel positioning is required with conventional RFA. These technical advantages increase the probability of successful denervation of neural pain generators that have variability in anatomic location. Additionally, a longer lesion of the RLP-generating nerve may be more reliably achieved with C-RFA compared to conventional RFA.

As such, the present study aims to define the attributable effect of cooled RFA on pain, physical function, and health-related quality of life in patients with post-amputation neuroma-associated residual limb pain. This prospective single-arm pilot study is intended to inform a future properly powered randomized controlled trial.

## Purpose and Objectives

---

### Objectives:

To assess changes in pain, physical function, and health-related quality of life in patients with post-amputation neuroma-associated residual limb pain after cooled radiofrequency ablation.

## Study Population

---

**Age of Participants:** >18 years old on the day of enrollment

### Sample Size:

At Utah: 20  
All Centers: 10

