### **Recruitment/Participant Identification Process:**

**In-PERSON CONTACT:** Participants will be recruited from the practices of the Principle Investigator and the Co-Investigators, the clinics of the University of Utah Orthopaedic Center, University of Utah Farmington Clinic, and the University of Utah South Jordan Health Center, and other University of Utah Hospital and Clinic locations. If the participant appears to be a candidate, he or she will be invited to participate.

**WRITTEN OR ELECTRONIC CHART REVIEW** will also be used to identify potential study participants on the PI and Co-PIs clinical and procedure schedules. The PI, Co-PIs, Clinical Research Coordinator, and Study Coordinator will perform the chart review to determine eligibility.

**REFERRALS:** Additional recruitment from University of Utah Hospitals and Clinics and local prosthetic offices. Flyers will be posted and information readily available for primary care providers to refer to the PM&R spine clinic. Flyers will be posted in waiting rooms, and clinic bulletin boards.

Participants will be personally invited to participate by either the PI or the Co-PI's either in person while in their respective clinics.

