**Informed Consent:**

**Description of location(s) where consent will be obtained:**

Consent will be obtained at one of these University of Utah clinic locations: University of Utah Orthopaedic Center University of Utah South Jordan Health Center University of Utah Farmington Health Center

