**SOC Cooled Radiofrequency ablation (C-RFA) of Residual Limb Neuroma Procedure:**

*C-RFA:*

Our RFA procedures will be performed similar to methods described by Zhang et. al and Kim et. al with modification accounting for appropriate C-RFA technique. This technique is currently standard clinical practice at University of Utah outpatient clinic sites. During the C-RFA procedure, the participant will be positioned prone. The participant's skin will be prepared with chloroprep. An ultrasound probe will be placed on the participants' residual limb at a transverse angle in order to view the nerve and associated neuroma in long-axis. The probe will be advanced to the site of the stump neuroma. An 18-gauge C-RFA electrode with a 4mm active tip (Coolief® Cooled Radiofrequency Kit, Avanos Health Inc, Alpharetta, GA) will be placed adjacent to the neuroma. This needle will be connected via wire to a cooled radiofrequency generator. Motor testing will be performed (2.0 V, 2Hz). Sensory testing will be performed (1.0 V, 50Hz) to reproduce or exacerbate the RLP and / or PLP. At the site of the neuroma, 2 mL of local anesthetic will be injected through the needle (without triamcinolone as used per Zhang study). When the local anesthetic demonstrates pain relief, the needle will be placed into the nerve. C-RFA lesions will be created by using the typical C-RFA protocol with lesions performed for 165 seconds, with the RFA generator temperature set to 60°C (intralesional temperature >80 degrees). Once the procedure is completed, the needle will be removed. Following ablation, 0.5 mL of 0.5% bupivacaine will be injected at the site of the ablated neuroma to provide post procedure analgesia. No corticosteroids will be injected.

Following the Standard Treatment Procedure visit, routine scheduled follow-up will occur at 1 month (+/- 1 week), 3 months (+/- 2 weeks), 6 months (+/- 2 weeks), and 12 months (+/- 2 weeks) at which times all follow-up measures will be obtained. These questions will be administered over the phone or be sent to you using a secure REDCap survey by email. If received by email it will be in the form of two e-mail links in which you will again be asked questions regarding your pain level, changes in activity limitations, symptoms, emotions and

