### **Data Analysis Plan**

A categorical responder analysis will also be performed using >50% pain relief in PLP and RLP, as well as the minimally clinically important change (MCIC) for secondary outcome measures for which an MCIC has been defined, and >30% improvement for secondary outcome measures for which an MCIC has not yet been defined.

While there is no standard residual limb pain outcome recommendation, the NIH's recommendation on pain interventions was applied to this study. These secondary outcomes include PGIC score less than 3 (indicating "improved" or "very much improved"), a 6.8 or greater point reduction on the MQS III score (equivalent to approximately 10 daily morphine equivalents).

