### Statistical analysis

Means and standard deviations of participant demographic data, as well as pain, functional, and other outcome data will be calculated. Proportions and 95% confidence intervals will be calculated for categorical data.

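### The only stated sample size contradicts itself (20 at Utah, 10 across all centers), so the enrolment target is undefined

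*Combined protocol and SAP*

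**What the plan says.** The Sample Size entry under Study Population has two lines. The Utah line gives 20. The line below it reads "All Centers: 10". Nothing else in the protocol or its statistical section gives a planned number, a justification for one, or an allowance for dropout.

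The sections that describe where participants come from mention Utah only:

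- **Recruitment/Participant Identification Process:** beyond the investigators' own practices and clinics, it adds "Additional recruitment from University of Utah Hospitals and Clinics and local prosthetic offices". The prosthetic offices appear there as a source of participants, not as study centers.
- **Informed Consent:** "Consent will be obtained at one of these University of Utah clinic locations", followed by three University of Utah locations.
- **C-RFA procedure:** "This technique is currently standard clinical practice at University of Utah outpatient clinic sites".

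On purpose and analysis, the Introduction says: "This prospective single-arm pilot study is intended to inform a future properly powered randomized controlled trial". The Data Analysis Plan says: "A categorical responder analysis will also be performed using >50% pain relief in PLP and RLP". The Statistical analysis section says "Means and standard deviations of participant demographic data, as well as pain, functional, and other outcome data will be calculated", and then "Proportions and 95% confidence intervals will be calculated for categorical data".

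**The concern.** Read with their ordinary meaning, the two lines cannot both be true: the Utah participants are part of the all-centers total, and the part is larger than the whole. Both figures are plainly legible, and nothing suggests a redaction or a damaged table.

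This is the only place where planned enrolment is stated, and the two figures differ by a factor of two. As written, nobody can say whether the study has met, missed or exceeded its target. Nor can a reader tell how much information the pilot was meant to supply to the later randomized trial.

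**Working it through.** **1. Is there a calculation to reproduce?** No. The documents give no significance level, power, effect size, standard deviation, expected responder rate, target interval width or dropout rate. The check is therefore one of consistency.

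**2. Consistency.** The inputs are the two lines of the Sample Size entry. The requirement is all-centers total ≥ Utah count. With the figures put in, 10 ≥ 20, which is false. The total falls short of one of its own parts by 20 − 10 = 10 participants.

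**3. Can the rest of the text settle it?** Consent is taken at Utah clinics, the procedure is described as practice at Utah sites, and no other enrolling center is named. If Utah is the only center, the two lines should be equal, and planned enrolment is 10 or 20. Nothing in the text favours one over the other.

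**4. What does the ambiguity imply for precision?** The plan calls for 95% confidence intervals for categorical data, which include the responder proportions, so those are the intervals to compare. For continuous outcomes it plans means and standard deviations without intervals, so none is computed here.

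For x responders among n, the exact (Clopper-Pearson) 95% limits are:

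- lower = 2.5th percentile of Beta(x, n − x + 1)
- upper = 97.5th percentile of Beta(x + 1, n − x)

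At an assumed 50% rate, x = 5 for n = 10 and x = 10 for n = 20. The responder rates below are all assumptions, because the plan states none. All n participants are taken to contribute an outcome. Widths are in percentage points and come from unrounded limits.

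| Assumed rate | n = 10 | Width | n = 20 | Width | Ratio of widths |
|---|---|---|---|---|---|
| 30% | 6.7% to 65.2% | 58.6 | 11.9% to 54.3% | 42.4 | 1.38 |
| 50% | 18.7% to 81.3% | 62.6 | 27.2% to 72.8% | 45.6 | 1.37 |
| 70% | 34.8% to 93.3% | 58.6 | 45.7% to 88.1% | 42.4 | 1.38 |
| 80% | 44.4% to 97.5% | 53.1 | 56.3% to 94.3% | 37.9 | 1.40 |

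The ratios are close to the large-sample value √(20/10) = 1.41, as expected.

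**The case against.** The strongest reply is that this is a clerical slip with no bearing on the results. The study is a descriptive single-arm pilot with no power calculation to invalidate, no hypothesis test and no success threshold tied to the number enrolled. Whatever proportions are reported will be based on the participants actually analysed. All of that stands, and it limits how serious the point is. It does not remove the contradiction.

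A second reply is that other centers may exist. The separate all-centers line leaves room for them, and the opening page is not in the copy reviewed. That also stands in part: a Utah-only study is an inference from no other center being named, not something the protocol states. It does not rescue the entry, because a total over several centers still cannot be below the count at one of them.

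A reader might also infer that the second line means 10 participants at other centers, for a total of 20 + 10 = 30. That would remove the arithmetic conflict, but the label does not say it and no such center is described. The entry would need correcting even then.

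Finally, a reader might infer that the contradiction spoils a planned level of precision. The documents plan no precision: they give no target width, expected rate or standard deviation. The intervals above show only what each figure would imply under assumed rates, and settling on one number would not by itself create a precision target.

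**Conclusion.** The point holds in a limited form. The protocol's only statement of planned enrolment is impossible as written. The likely intended number is 10 or 20, on the inference that Utah is the sole center, and the documents do not show which.

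The cost is an undefined enrolment target. It also leaves a difference in implied precision of about 1.4 times in interval width for proportions, over assumed responder rates of 30% to 80% and with complete outcome data. A reader might go further and treat this as a flaw in the study's power or validity. The documents do not support that, because no test, threshold or power claim rests on the number. It should be corrected, but it is not among the faults that must be resolved before the results could be trusted.

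**What to change.** The sponsor should reconcile the Sample Size entry to one planned number. The all-centers total must be at least the Utah count, and the two should be equal if Utah is the only center. If other centers take part, the entry should give the number planned at each.

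If the study is Utah-only, this means correcting one figure, with no change to procedures or analysis. If there are other centers, the right total may be a figure that does not yet appear in the protocol. The recruitment and consent sections would then also need to name those centers.

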### Inclusion Criteria:

### Inclusion Criteria:

1. Age greater than 18 years of age at day of enrollment.
2. Clinical diagnosis lower extremity amputation performed more than 1 year since study enrollment.
3. .
4. Pain duration of more than 6 months despite a trial of conservative therapy (medications, physical therapy) for 2 months.
5. Ultrasound and / or MRI imaging pathology consistent with clinical symptoms and signs.
6. Greater than 50% pain relief with a diagnostic neuroma block

### **Exclusion Criteria:**

#### Exclusion criteria:

1. Refusal or inability to participate, provide consent, or provide follow-up information for the 12-month duration of the study.
2. Contraindications to diagnostic block or treatment ablation (active infection, bleeding disorders, and pregnancy or breastfeeding, active immunosuppression, participation in another phantom or residual limb pain trial within the last 30 days)
3. Non-neurogenic source of residual or phantom limb pain.
4. Active moderate to severe lumbar radiculopathy.
5. Any injection in the residual limb within the last 30 days.
6. Severe uncontrolled medical condition as determined by treating physician.
7. Severe psychological illness.
8. History of Inflammatory arthritis.
9. Malignancy within past 5 years except basal cell or squamous cell skin cancer.
10. Current opioid use exceeding 50 morphine milligram equivalents per day.
11. A history of alcohol or drug abuse within past 5 years.
12. Use of any investigational drug within past 30 days.
13. Pending litigation involving participant's residual limb pain.
14. Incarceration

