## **Procedures:**

Screening Visit: As participants are identified by the PI or CO-I's as being possible candidates for this study they will be invited to participate. Main inclusion requirement, as listed in inclusion criteria, is that the patient is being scheduled for residual limb neuroma radiofrequency ablation (RFA) procedure as standard of care. If patient states interest in the study and wishes to discuss in more detail a research coordinator will discuss at time of appointment or call and answer any questions at a time convenient to the patient. If patient is interested, and does meet inclusion/exclusion criteria, and does not have time to do the baseline questions at time of appointment a qualified research staff member will call the patient to complete by phone. It is anticipated that most subjects in this study will be identified mainly through the regular flow of the University of Utah clinics. The informed Consent process will occur either at the time the subject is in clinic or the participant may elect to complete the process at a later time. Eligibility is determined by the inclusion and exclusion criteria. Qualifying volunteers will be asked to provide both written and verbal informed consent once a standard of care treatment plan has been agreed upon by the patient and treating physician.

Baseline: Participants who meet inclusion and exclusion criteria will be enrolled into the study after consenting to participate and before receiving residual limb neuroma RFA. This procedure is considered standard of care and are typically based on physician preference. Baseline data will be collected within 2 weeks prior to the scheduled procedure, this will include information from their examination and baseline questionnaires which include the following:

An electronic data collection system (REDCap via computer) will be used to record all pre-procedure and follow-up data as listed above (See attached PDF for baseline survey)

1. Age (years).
2. Sex
3. Height (cm).
4. Weight (Kg).
5. Duration of pain (weeks).
6. Date of amputation
7. Etiology of amputation
8. Level of amputation
9. Radiologic diagnosis based on ultrasound of residual limb.
10. Patient-Reported Outcomes Measurement Information System (PROMIS) 10
11. Analgesic medication log: dose and frequency of each medication
12. Brief Pain Inventory (BPI) with modification to include numerical rating scale (NRS) score (worst, least, average, current).

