**Procedures performed for research purposes only:**

1. survey/questionnaire

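### Does the 30-day injection exclusion shut out patients because of the diagnostic block they must have had?

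*Combined protocol and SAP*

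**What the plan says.** Inclusion criterion 6 asks for "Greater than 50% pain relief with a diagnostic neuroma block". It gives no date or window for the block.

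Exclusion criterion 5 bars "Any injection in the residual limb within the last 30 days". It names no exemption and no reference date. Exclusion criterion 2 covers "Contraindications to diagnostic block or treatment ablation", so the block and the ablation appear together in one contraindication item.

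The Procedures section fixes the order of events. At screening, the main requirement is that "the patient is being scheduled for residual limb neuroma radiofrequency ablation (RFA) procedure as standard of care". Consent is taken "once a standard of care treatment plan has been agreed upon by the patient and treating physician". Then: "Participants who meet inclusion and exclusion criteria will be enrolled into the study after consenting to participate and before receiving residual limb neuroma RFA". On timing before ablation it adds: "Baseline data will be collected within 2 weeks prior to the scheduled procedure".

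The section headed "Procedures performed for research purposes only" has one entry, the survey or questionnaire. The Statistical analysis section is descriptive throughout.

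**The concern.** The protocol requires a procedure that one of its own exclusions, read word for word, catches. Enrollment has to come after the block, because its result is an entry criterion, and before the ablation. If the 30 days run back from enrollment, baseline or procedure, the clinic's interval between block and ablation becomes an unwritten entry criterion. A patient whose routine ablation follows soon after the block could not be enrolled at all. If the block is exempt, or the check is made at a screening date before the block, the same patient is eligible.

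Two careful readers could therefore classify one patient in opposite ways. At stake are recruitment into a very small pilot and the chance that an enrollment accepted by site staff is later counted as a protocol deviation.

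**Working it through.** The plan states no figure on this point, so there is none to reproduce. The check is a day count.

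**Inputs.** The 30-day window comes from exclusion 5. The 2-week (14-day) baseline window and the rule that enrollment precedes ablation come from Procedures. The interval *d* from block to ablation is not in the documents, so a range is shown.

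**Literal reading.** Put the block on day 0, ablation on day *d* and enrollment on day *e*. The block is within the last 30 days while *e* ≤ 30, so an eligible day needs 30 < *e* ≤ *d*.

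- Eligible days counting the day of ablation: max(0, *d* − 30).
- Eligible days strictly before the day of ablation: max(0, *d* − 31).
- If day 30 itself is allowed (*e* ≥ 30), each count moves by one: max(0, *d* − 29) and max(0, *d* − 30).

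| *d* (assumed) | Day 30 excluded: incl. ablation day / before it | Day 30 allowed: incl. ablation day / before it |
|---|---|---|
| 7, 14, 21, 28, 29 | 0 / 0 | 0 / 0 |
| 30 | 0 / 0 | 1 / 0 |
| 31 | 1 / 0 | 2 / 1 |
| 35 | 5 / 4 | 6 / 5 |
| 44 | 14 / 13 | 15 / 14 |
| 45 | 15 / 14 | 16 / 15 |

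**Baseline window.** The whole of it lies clear of the exclusion when *d* − 14 > 30, that is from *d* = 45, or from *d* = 44 if day 30 is allowed.

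**Block exempt, or window checked before the block.** Every day from block to ablation qualifies, *d* + 1 days counting both ends: 8 for *d* = 7, 15 for *d* = 14, 31 for *d* = 30.

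**What the count shows.** The two readings part company for *d* up to about 30 days, and the exact edge depends on how day 30 is treated. For longer intervals a patient can meet both criteria under either reading. The count cannot show that any patient falls in the affected range, because nothing in the documents gives *d*.

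**What the other passages add.** Exclusion 2 states no sequence. It could mean that screening begins before the block, in which case exclusion 5 can be checked then and the conflict disappears. Consent only after an agreed treatment plan points instead to the block coming first. The research-only list says nothing about who sets the ablation date. It may also be incomplete, since the baseline items include von Frey and algometer testing, which are not surveys. These passages do not settle which reading was meant, and they do not show that ablation follows the block within 30 days.

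**Effect on results.** The analysis has no comparison between arms and no hypothesis test that depends on this criterion. Followed literally, exclusion 5 is a washout. With the block exempt, the study admits patients with a more recent block. In both cases the summaries describe the patients enrolled.

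**The case for a change.** The best case for a change is that *any* leaves no room for an implied exemption, and that exclusion 5 differs from the other undated look-backs (exclusions 2, 9, 11 and 12) because it alone catches something the protocol requires. The drafters did tie dates to enrollment in inclusion criteria 1 and 2, so the omission here is noticeable. The local anesthetic given during the ablation cannot serve as the qualifying block, since it comes after enrollment. The listed baseline items do not include the block date, so compliance could not be checked from them. The Sample Size section gives 20 for Utah and 10 for all centers, so one disputed patient is 1/20 = 5% or 1/10 = 10%. A pilot meant to inform a randomized trial should pass on an entry rule that others can reproduce. Clarifying it would cost a sentence and a date field.

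Most of this stands as an account of the wording, and a clarifying note would do no harm. It does not show that the plan as written goes wrong. The criteria can be met together, no affected patient can be identified from the documents, and no estimate is shown to be biased. What is requested is that the investigators write down which of two workable readings they meant. The low cost is also not quite as low as it looks: if the block were declared to count, the usable baseline days would shrink for *d* below 45, and recruitment could slow.

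**Conclusion.** The ambiguity is real but minor: a gap in drafting that the site can fill sensibly, not a contradiction. Its reach is limited to patients ablated within about 30 days of the block, and then only if the block counts and the window runs back from enrollment, baseline or procedure. The share of such patients cannot be derived from the documents. The consequence would be a lost recruit or a disputed deviation, with no demonstrated effect on the descriptive results.

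This rests on three assumptions: the investigators apply one reading to all patients; the visible criteria are substantially complete, although inclusion item 3 is blank in the text available; and, if the block is treated as exempt, baseline pain is not recorded while the block is still acting. Which reading applies is for the investigators. No change to the plan is needed.
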